## 247      **Chapter 3: Study Procedures and Data Collection**

### 248      **3.1 Overview**

249      Training and data collection for the study will be completed remotely. Study supplies will be sent  
250      to the participant by mail. Participants will be followed for up to 12 months or until they  
251      discontinue CGM use. After initial CGM training has been completed, participants will continue  
252      to be followed by the virtual clinic team for six months. After the initial six months of follow up,  
253      participants who decide to continue to use CGM will be asked to extend follow up for an  
254      additional 6 months and complete questionnaires, submit HbA1c samples, and share CGM data.  
255      During the extended follow up phase, participants will be able to contact the virtual clinic with  
256      questions or to request assistance as needed.

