## PROTOCOL SUMMARY

PARTICIPANT AREA	DESCRIPTION
Title	Virtual Diabetes Specialty Clinic: A Study Evaluating Remote Initiation of Continuous Glucose Monitoring
Précis	This study will assess feasibility and efficacy of establishing a virtual diabetes clinic with a focus on introduction of CGM technology and ongoing CGM use to minimize such rate-limiting factors as geography, cost and access to specialty care
Objectives	The objective of this study is to evaluate a virtual diabetes clinic model, for adults with either T1D or T2D, that supports integration of CGM into diabetes self-management and evaluates use of decision support technology within the virtual clinic model.
Study Design	Single-arm prospective longitudinal study

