## 1 SCHEDULE OF STUDY VISITS AND PROCEDURES

2 This is a remote study design with virtual visits; eligibility and other study questionnaires are by participant self-report.

3

	Enrollment	Initial Virtual Clinic Contact	Baseline CGM Data Collection	Virtual Clinic Training Phase (0-13 Weeks)					Virtual Clinic Follow Up Phase	Optional Extended Participant Follow Up	
				Training 1 (Week 0)	Training 2 (Week 1)	Training 3 (Week 3)	CGM Follow Up (Weeks 4, 8)	CGM Follow Up (Week 13)			
TARGET WINDOW		Within 7 Days from Completion of Enrollment Questionnaires		Day 0	Day 7-14	Day 21-28			Weeks 12-14		
ICF • Eligibility Confirmation	X									X*	X*
Baseline Data Collection • Contact Information • Demographics • Medical History • Questionnaires	X		X								
Follow-Up Data Collection**					X	X	X	X	X	X	X
HbA1c***			X					X	X	X	X
Video Tutorials / Access to Resource Materials		Examples: CGM Overview Parts of CGM	Examples: HbA1c Sample Collection CGM Setup	Examples: Understanding Your Real-Time Data How to Change Sensor	Examples: How to Upload CGM Data How to View Reports Understanding Your Ambulatory Glucose Profile / Data Patterns	X	X	X	X	X	X
Contact with Study Team†		X	X	CGM Initiation	CGM Data Interpretation	CGM Data Review Goal Setting	X	X	X	X	X
CGM Use††			~2 Week Blinded CGM Use †††	Start of 26-Week Unblinded CGM Use	X	X	X	X	X	X	X

\*. Participants will be asked to extend follow up for an additional 26 weeks and sign an addendum ICF if they plan to continue to use CGM after the first 26 weeks. Virtual Clinic follow up will be available to participants on an as-needed basis after the first 26 weeks.

\*\*Participants will be asked to complete questionnaires monthly after CGM Initiation. A final questionnaire will be elicited at the earlier of CGM discontinuation or completion of study follow up (~52 weeks).

\*\*\*HbA1c checks prior to unblinded CGM initiation, and at 3-month intervals following CGM initiation (~13 weeks, 26 weeks, 39 weeks, and 52 weeks)

†Follow up may be via phone, text, virtual (i.e. Skype), or app. outside of scheduled training. Additional follow up may be conducted as needed. Participants may follow up with study team as needed.

††CGM supplied for blinded data collection will be provided. CGM supplies for six months of unblinded use will be provided for those who successfully complete blinded data collection.

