### 425      **6.2 Sample Size**

426      The goal for the study is to include at least 300 participants who initiate training for CGM. This  
427      is a convenience sample and not based on statistical principles.

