7.3 Missing Data

Missing data will not be imputed for any outcomes in this study and will be handled by means of direct likelihood analyses.

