7.4 Statistical Methods

For all outcomes, summary statistics appropriate to the distribution will be tabulated on a subject level overall and within the subgroups defined in Section 12. For the CGM metrics, summary statistics appropriate to the distribution also will be tabulated for each 4-week interval and for the first and last 26 weeks of the study. For the questionnaires, summary statistics will be reported for the mean scores in addition to the individual responses for each question.

For all outcomes, a linear mixed model with a random subject effect will be used to test whether the mean change from baseline significantly differs from zero. These models will be fit for each of the subject level CGM metrics and HbA1c at 13, 26, 39, and 52 weeks. They also will be fit for the questionnaires at 26 and 52 weeks. If values are skewed, then winsorization will be utilized. Point estimates and 95% confidence intervals for change in glycemic outcomes will be reported.

For the three mental health screening questionnaires, only summary statistics will be tabulated. The three mental health screening questionnaires falling under this umbrella are the Patient

187 Health Questionnaire-8, the Diabetes Distress Scale (Management Distress Subscale), and the
188 Fear of Hypoglycemia Survey (Worry Subscale).

189 **7.5 Analyses Windows**

190 For HbA1c, only measurements occurring within ± 45 days of the target measurement date at a
191 given time point will be included in the tabulation of summary statistics. The windows for
192 glycemic metrics were defined above in Section 7.1.

193 **7.6 Sensitivity Analyses**

194 For CGM and HbA1c outcomes, a complete-case analysis restricting to non-missing outcomes
195 will also be assessed. A paired t-test (for normally distributed outcomes) or a Wilcoxon signed
196 rank test (for skewed outcomes) will be used.

197 **8 Safety Analyses**

198 All adverse events that occur on or after the date of enrollment will be listed in a table.

199 For events occurring on or after the date of CGM initiation, the reported safety outcomes include
200 diabetic ketoacidosis (DKA), severe hypoglycemia (SH), hospitalization, and emergency room
201 visits. The following statistics will be tabulated for each safety outcome:

- 202 • Total number of events
- 203 • Number and proportion of subjects with an event (discretized into bins)
- 204 • Incidence rate per 100 person years

205

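### HbA1c and questionnaires stop when CGM stops, so the 39- and 52-week changes rest on a missing-at-random assumption that no planned analysis tests

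*Protocol*

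**What the plan says.** Protocol 3.1 ties the end of follow-up to device use: "Participants will be followed for up to 12 months or until they" stop using CGM. For months 7 to 12 it says "participants who decide to continue to use CGM will be asked to extend follow up for an", and the next line continues "additional 6 months and complete questionnaires, submit HbA1c samples, and share CGM data". Protocol 2.1.1 and the schedule footnote likewise seek the addendum consent from those who plan to keep using CGM.

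At stopping, the schedule asks for one last questionnaire: "A final questionnaire will be elicited at the earlier of CGM discontinuation or completion of study follow up". No HbA1c is named there, nor among the items requested at withdrawal (Protocol 5.5).

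On analysis:

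- SAP 6.1 admits to the HbA1c and questionnaire analyses anyone with any relevant value after CGM initiation.
- SAP 7.3 states "Missing data will not be imputed for any outcomes in this study" and relies on direct likelihood.
- SAP 7.4 fits mixed models with a subject random effect, for HbA1c at 13, 26, 39 and 52 weeks and for questionnaires at 26 and 52 weeks. The three mental health screening scales are only summarised.
- SAP 7.6 is the only missing-data sensitivity analysis: "For CGM and HbA1c outcomes, a complete-case analysis restricting to non-missing outcomes". It does not mention questionnaires. The winsorization in SAP 7.4 deals with skewness.

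**The concern.** HbA1c comes from a fingerstick sample posted to a laboratory, and the questionnaires are completed on a website. Apart from the surveys about CGM itself, neither depends on wearing a sensor. Ending their collection when CGM stops creates missing data that could have been avoided, and the missingness is linked to giving up part of the intervention.

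The stated objective is to evaluate a clinic model meant to reduce barriers such as cost and access. People who stop CGM are part of that answer. Loss is most likely after week 26: free supplies end at six months, further use depends on insurance approval (Protocol 5.3), and the extension needs a new consent. At stake is whether the 39- and 52-week changes can be read as applying to everyone who initiated CGM. Event reporting is affected too, because person-years in SAP section 8 end with study follow-up.

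**Working it through.** **No planned figure to reproduce.** The design is a "Single-arm prospective longitudinal study", and the target of 300 "is a convenience sample and not based on statistical principles". The documents give no dropout rate, expected HbA1c change or SD for this trial. Everything below rests on assumed values and shows size only.

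**Step 1: which values can exist.** Someone who stops before week 26 gives no scheduled HbA1c after stopping. Someone who stops at week 26 gives none at 39 or 52 weeks. All 39- and 52-week HbA1c values therefore come from continuers.

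**Step 2: what each analysis estimates.** The mixed model keeps the earlier values of those who stopped and, under missing at random, estimates late change as if they had stayed on CGM. Anyone with no HbA1c after initiation drops out. Complete-case uses continuers alone and needs a stronger assumption.

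**Step 3: simple mixture.** Let d be the share who stop, Dc the change in continuers and Dd the change in those who stop. Then

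overstatement of a continuer-only mean = d × (Dd - Dc).

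Assume Dc = -1.0 HbA1c point.

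| d | Dd = -1.0 (all kept) | Dd = -0.5 (half kept) | Dd = 0 (all lost) |
|---|---|---|---|
| 10% | 0.00 | 0.05 | 0.10 |
| 20% | 0.00 | 0.10 | 0.20 |
| 30% | 0.00 | 0.15 | 0.30 |
| 40% | 0.00 | 0.20 | 0.40 |

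For example, 0.4 × (0 + 1.0) = 0.40.

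**Step 4: the planned analyses.** The simulation has 200,000 participants at 0, 13, 26, 39 and 52 weeks. Assumed values:

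- means on CGM of 8.5, 7.7, 7.5, 7.5 and 7.5;
- between-person SD 1.2, SD of individual response 0.6, residual SD 0.5;
- a share d stops after week 26, chosen as the worst 13-week change plus noise of SD 1.

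The random-intercept model was fitted by generalised least squares with fixed variance components. The 52-week changes were:

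| d | Course after stopping | All participants | Mixed model | Complete-case |
|---|---|---|---|---|
| 10% | unchanged | -1.001 | -1.021 | -1.089 |
| 20% | unchanged | -0.996 | -1.032 | -1.153 |
| 30% | unchanged | -0.999 | -1.050 | -1.222 |
| 40% | unchanged | -1.000 | -1.065 | -1.287 |
| 10% | back to baseline | -0.948 | -1.021 | -1.089 |
| 20% | back to baseline | -0.874 | -1.036 | -1.156 |
| 30% | back to baseline | -0.791 | -1.052 | -1.223 |
| 40% | back to baseline | -0.707 | -1.072 | -1.295 |

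Overstatement by the mixed model:

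- Course unchanged: 1.021 - 1.001 = 0.020 at 10%, rising to 1.065 - 1.000 = 0.065 at 40%. Missing at random holds here. The small remainder reflects a random-intercept covariance that does not match the simulated variation in response.
- Back to baseline: 1.021 - 0.948 = 0.073 at 10%, then 0.162, 0.261, and 1.072 - 0.707 = 0.365 at 40%.

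**Step 5: can the sensitivity analysis tell the two apart?** The gap between complete-case and mixed model is 0.068, 0.121, 0.172 and 0.222 when the course is unchanged, and 0.068, 0.120, 0.171 and 0.223 when benefit is lost. The gaps are practically identical, while the all-participant change at 40% differs by 1.000 - 0.707 = 0.293. In every row complete-case lies further from the all-participant value than the mixed model does.

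**The case against.** Several points on the other side stand.

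- A reader might infer that the late results describe continuers only. That is true of the observed summaries and the complete-case analysis. The mixed model retains earlier values from those who stop.
- A reader might conclude that the clinic's effect is overstated. The documents do not establish this. It requires those who stop to do worse afterwards than the model predicts, and no data in the documents address that. With a single arm, change from baseline would not isolate the clinic's effect even with full follow-up.
- A reader might expect the two analyses to agree and so reassure falsely. They differ by 0.07 to 0.22 point here. The fault is that their difference carries no information about what happens after stopping.
- The shortcut p/(1-p) for a share p who stop gives 11% at 10% and 67% at 40%. It matches neither planned analysis when poor responders stop more often. In the return-to-baseline rows the mixed model overstates by 0.073/0.948 = 8% and 0.365/0.707 = 52%, and complete-case by 0.141/0.948 = 15% and 0.588/0.707 = 83%.
- CGM metrics cannot exist after CGM stops. Some losses will be administrative, through insurance or declined consent.
- Discontinuation is a reported outcome, overall and by subgroup (SAP 5 and 12), with a survey of reasons. Protocol 1.1 cites about 90% daily or near-daily use at six months in earlier studies. The SAP calls all analyses exploratory and names no primary outcome.

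These limit scope and severity but do not remove the point. A discontinuation rate says how many stopped, not what their HbA1c became. The 90% figure says nothing about month 12. Exploratory or not, 39- and 52-week HbA1c changes will be tested and reported with confidence intervals.

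**Conclusion.** The point holds for HbA1c and questionnaires, chiefly at 39 and 52 weeks and after any earlier stop. These data are missing by design once CGM stops. The main estimate rests on missing at random, and the planned sensitivity analysis cannot test it. For questionnaires, SAP 7.6 provides none.

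Late change may be overstated for all who initiated CGM. On the assumed inputs, the mixed-model error is small (0.02 to 0.07 HbA1c point) if benefit persists after stopping, and 0.07 to 0.37 point at 10% to 40% discontinuation if it is fully lost. The second range is an extreme case. Both depend on the assumed mean change of -1.0, the assumed SDs, and poor early responders stopping more often. A change worth making, proportionate to an exploratory study.

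**What to change.** 1. **Data collection.** Amend Protocol 3.1, the schedule and the extension consent so that participants who stop CGM without withdrawing consent still receive the scheduled HbA1c kits, questionnaires and event reports. Offer the extension to everyone. This concerns data collection only. Surveys about CGM itself can end with CGM use.
2. **Analysis.** In SAP 7.6 add, for HbA1c and the questionnaires modelled under SAP 7.4, a missing-not-at-random analysis of values missing after CGM discontinuation. Use a delta-adjusted range with return to baseline as the extreme, by multiple imputation so that uncertainty is kept. Amend SAP 7.3, and the no-imputation remark that closes SAP 7.2, to allow this analysis only. State whether the late estimate refers to everyone who initiated CGM or to a setting in which all had continued.

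CGM metrics need no change.

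Step 1 costs a short amendment with IRB review and consent changes, and at most four already planned kits per person who stops. Step 2 is SAP wording and programming, and remains worthwhile if step 1 is no longer possible. The late estimate may look less favourable.

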### 257      **3.2 Virtual Clinic Team Interactions with Study Participant**

258      Each participant will be assigned to work with virtual clinic team members who are able to  
259      provide clinical care for diabetes management in the state where the participant resides. The  
260      virtual clinic team members will teach participants to use and incorporate CGM into self-  
261      management practices. Mental health service support options for diabetes-related mental health  
262      issues will be discussed as needed.

263      The virtual clinic team will assist with initiation of CGM, as needed, after CGM supplies are  
264      received and will provide additional training after approximately one week of CGM use, and  
265      after approximately three weeks of CGM use. Virtual clinic team members will check in with  
266      participants during study follow up to review CGM data and recommendations related to  
267      diabetes management, and additional virtual visits may be scheduled. Contact with a virtual  
268      clinic team member may be requested by the participant at any time.

269      In addition, the virtual clinical team member will follow up with the study participant if there is  
270      an elevated score on the psychosocial screening questionnaires (section 2.8). The virtual clinic  
271      team will follow their internal processes for diabetes related mental health services support.  
272      Participants may be offered the opportunity to work with a behavioral health coach from the  
273      virtual clinic team at no cost. Follow up communication with a personal healthcare provider is at  
274      the discretion of the virtual clinic for any issues which may require additional support.

275      The virtual clinic team member(s) may interact with the participant through texts, emails, phone  
276      calls and/or virtual training sessions. Phone calls may be recorded. Additional mobile  
277      applications may be required to facilitate communications between participant and virtual clinic  
278      team member(s) depending on program enrollment.

#### 279      **3.2.1 Virtual Clinic Team Interactions with Personal Healthcare Provider**

280      Communications will be provided to the health care provider whom the participant designates for  
281      diabetes management, so that the provider is aware of the participant's study participation and of  
282      information related to care or treatment (See section 3.5.2).

### 283      **3.3 CGM Initiation (Unblinded Use)**

284      CGM supplies will be sent to the participant by mail. Device user manuals will be provided  
285      along with study instructions. The study website will include a resources page which may

286 include device user manuals, study instructions and tutorials, and links to standard of care  
287 diabetes-related educational information recommended by the study team. Live webinars may be  
288 available for those who want to receive additional education about diabetes management and use  
289 of CGM technology.

290 A virtual training session will be arranged with the participant's virtual clinic team member to  
291 answer questions regarding CGM set up, sensor insertion, alerts and alarms, uploading data, and  
292 visualizing data.

293 **3.4 CGM Use and Data Interpretation**

294 After the initial training to initiate CGM use, participants will receive additional training on how  
295 to use data visualization tools and how to use the CGM data to make self-management changes  
296 in insulin dosing, meals, exercise, etc. The training approach may vary by participants' age  
297 and/or comfort with technology.

298 **3.5 Insulin Dose Changes**

299 If the virtual clinic team believes that changes in insulin type or dosing should be considered,  
300 they will work with the participant to implement any such changes.

301 **3.5.1 Decision Support**

302 Decision support tools, which include use of a mobile application, may be used, if available, to  
303 provide the virtual clinic team with potential recommendations regarding insulin use. The virtual  
304 clinic team will review all data, including any available decision support recommendations,  
305 before making recommendations. Use of decision support for T1D is approved for  
306 recommendations to providers. Use for T2D is investigational. For both T1D and T2D, use of  
307 decision support would be classified as a Non-Significant Risk as the decision support  
308 recommendation is made to the provider and does not replace virtual clinic team review of all  
309 available CGM and insulin data when considering management decisions.

310 **3.5.2 Personal Healthcare Provider Notification**

311 The health care provider whom the participant designates for diabetes management will be  
312 informed of insulin dose and other medication changes.

313 **3.6 Follow-up Data Collection**

314 Data will be collected throughout study follow up and will include information related to  
315 diabetes management, psychosocial outcomes, adverse event and device issues, patient-related  
316 outcomes and questionnaires, HbA1c measurement, and upload of device data.

317 **3.6.1 HbA1c**

318 HbA1c will be collected at approximately 13, 26, 39, and 52 weeks and measured at a central  
319 laboratory. A kit, which will include a blood collection tube and shipping materials, will be sent  
320 to the participant to obtain a fingerstick blood sample and return the sample to the lab.

321 **3.7 Data Uploads**

322 Instructions for downloads and data sharing from diabetes-related care devices and applications  
323 used for the study will be reviewed with each participant as part of their training.

324 **3.8 Insulin Delivery and Collection of Insulin Data**

325 Participants will use their own insulin during the study. If the participant uses an insulin pump,  
326 training will include uploading (or linking) of these devices.

327 MDI users with a compatible insulin pen may be given a Biocorp Mallya (Mallya) device to use  
328 during the study that automatically logs insulin dose. Mallya is a data collection device that  
329 automatically captures data such as date of injection, time of injection, insulin type, and dose.  
330 Mallya attaches directly to the insulin pen and does not alter how the pen is used. Mallya is  
331 intended for data collection purposes only, with minimal information communicated to the  
332 participant via the app or device. Mallya is an investigational device, and it is classified as a  
333 Non-Significant Risk device by the Sponsor.

334 An app that is needed to transfer data from the device used to log insulin dose will be installed  
335 on the participant's personal smartphone. Participants will be trained on use of the device and  
336 app as needed. If a device that automatically logs insulin dose is not available, the participant  
337 may be asked to enter insulin doses directly through an app.

338

## Chapter 4: Questionnaires

339 Questionnaires are completed by all participants on the study website. The responses to the  
 340 outcome surveys are not monitored in real-time. The procedures for administration are described  
 341 in the study procedures manual.

Measure	DESCRIPTION
Patient Health Questionnaire- 8	8-item survey to evaluate depression-related symptoms; 3 minutes to complete
Diabetes Distress Scale (Management Distress Items)	17-item management burden scale to measure the degree of distress related to diabetes; 4 minutes to complete.
Fear of Hypoglycemia (Worry)	6- item survey to measure concerns about low blood sugar; 2 minutes to complete
CDC Healthy Days	4 questions developed by the CDC to obtain a general assessment of physical and mental health; 2 minutes to complete
Hypoglycemia Confidence	Presents 8 common situations where hypoglycemia occurs and evaluates level of confidence of how it can be managed in those situations; 4 minutes to complete.
Diabetes Technology Attitudes	5-item survey to measure perceptions about the benefits of diabetes technology and devices; 2 minutes to complete.
Glucose Monitoring Satisfaction	15-item survey to evaluate treatment satisfaction/burden; 4 minutes to complete.
Sleep	1-item sleep survey that measures quality of sleep; 1 minute to complete
Benefits and Burdens of CGM	16 items per section with 2 sections that list situations (e.g. ability to share data, glycemic events, physical activity) and designation of whether they are barriers or benefits; 4 minutes to complete.
CGM Discontinuation	3-item survey; participants who discontinue CGM will be asked to complete this.

342 Participants may also be asked to answer questions, which have been approved by the IRB,  
 343 regarding their participation experience.

